## **4.6. Study Termination**

The investigator retains the right to terminate study participation at any time, according to the terms specified in the study contract. The investigator is to notify the institutional review board (IRB)/independent ethics committee (IEC) in writing of the study's completion or early termination, send a copy of the notification to the sponsor or sponsor's designee, and retain 1 copy for the site study regulatory file.

## **5. TREATMENT**

INCB059872 will be self-administered orally QOD or QD on a 28-day cycle. In each cycle of the QOD dosing schedule, subjects should receive 14 doses of INCB059872. In each cycle of the QD dosing schedule, subjects should receive 28 doses of INCB059872. Tablets will be available in 1 mg strength. The initial starting dose for Part 1 will be 2 mg QOD. The initial starting dose for other parts of the study will be based on the aggregate data review of Part 1.

For QOD administration, if a dose is missed by more than 24 hours, the subject should skip the dose and take the next scheduled dose at the usual time. For QD administration, if a dose is missed by more than 4 hours, the subject should skip the dose and take the next scheduled dose at the usual time. INCB059872 tablets should be taken on an empty stomach if possible (refrain from food consumption during the period 2 hours before and 1 hour after taking INCB059872). For subjects participating in the food-effect portion of the study in Part 2, TG B1, a high-fat, high-calorie meal will be consumed within 30 minutes before taking INCB059872 on Cycle 2 Day 1.

Alternative dosing regimens (ie, QD) may be explored based on emerging PK/█ and safety data.

### **5.1. Treatment Assignment**

#### **5.1.1. Subject Numbering and Treatment Assignment**

Study sites will enter subject demographic and baseline data into the Interactive Response Technology (IRT) in order to receive a subject number at the time of the subject enrollment. Sites will have to update the IRT system at each visit in order to receive the treatment allocation.

All subject numbers will be 6 digits; the first 3 digits will be the site number, and the last 3 digits will be the subject's number. This subject number will be maintained throughout the study and will not be reassigned. Subjects who withdraw consent or discontinue from the study after being assigned a subject number will retain their initial number.

This is a nonrandomized study; subjects will be assigned the same dose and treatment regimen in a particular treatment group. The investigator or designee will pull the correct number of bottles of study drug from their stock and dispense the study drug to the subject. All subsequent dispensing of study drug should follow this process. Refer to the IRT manual for detailed information.

For subjects who signed an ICF but are not allocated and for subjects who are allocated but were not treated, refer to the eCRF Completion Guidelines for instruction on which eCRFs to complete.

### **5.1.2. Randomization and Blinding**

Not applicable.

## **5.2. Study Drug Materials and Management**

### **5.2.1. INCB059872**

#### **5.2.1.1. Supply, Packaging, and Labeling**

Study drug will be supplied as 1 mg tablets of INCB059872. All tablet excipients comply with the requirements of the applicable compendial monographs (Ph Eur, USP/NF; refer to the [IB](#)).

INCB059872 will be provided as 1 mg tablets packaged in high-density polyethylene bottles. No preparation is required.

All Incyte investigational product labels will be in the local language and will comply with the legal requirements of each country and will state "Caution: New Drug--Limited by Federal (or United States) law to investigational use."

#### **5.2.1.2. Storage**

Bottles of tablets should be stored in a refrigerator and maintained at a temperature between 2°C and 8°C (36°F to 46°F).

#### **5.2.1.3. Instruction to Subjects for Handling Study Drug (INCB059872)**

The subject must be instructed in the handling of study drug as follows:

- To store the study drug in the refrigerator.
- To only remove from the study drug bottle/kit the number of tablets needed at the time of administration.
- Not to remove doses in advance of the next scheduled administration.
- To make every effort to take doses on schedule.
- To report any missed doses.
- To take study drug immediately upon awakening or 2 hours after completing a meal with a glass of water.
- If the subject vomits after taking study drug, the subject should not take another dose.
- To keep study drug in a safe place and out of reach of children.
- To bring all used and unused study drug kits to the site at each visit.
- Subjects who do not take their dose in the morning as instructed should plan to take the dose in the evening, with the same fasting parameters applied.

- If a dose is missed by more than 24 hours on a QOD schedule, that dose should be skipped, and the next scheduled dose should be administered at the usual time.
- If a dose is missed by more than 4 hours on a QD schedule, that dose should be skipped, and the next scheduled dose should be administered at the usual time.

## **5.2.2. Conventional Care Drugs**

Every effort should be made by the sites to procure the commercially available and packaged product. However, Incyte will provide certain reference therapy or therapies, such as tretinoin capsules or azacitidine or nivolumab where required by applicable law or regulation or under other limited circumstances when a subject may not otherwise have access to the therapy or therapies.

### **5.2.2.1. Tretinoin Capsules**

In Parts 3 and 4 TG C and TG C1, Tretinoin (ATRA) capsules will be administered as an open-label commercial product in accordance with local prescribing information at a dose of 45 mg/m^2 per day. The daily dose should be administered as 2 evenly divided doses. Drug is available in 10 mg capsules and should be stored in accordance with the package insert. Toxicity associated with tretinoin capsules will be managed per instruction in the package insert.

### **5.2.2.2. Azacitidine**

In the Parts 3 and 4 TG D and TG D1, azacitidine will be administered in accordance with local prescribing information as an open-label commercial product at a starting dose of 75 mg/m^2 SC or IV for 7 days during the first 9-day or less period (ie a 2-day break allowed on weekend, if needed) of each 28-day treatment cycle. Toxicity associated with azacitidine dosing will be managed per instructions in the package insert ([Vidaza PI 2014](#)).

Investigative sites must provide subjects with administration and storage instructions, as per package insert or institution standard, for azacitidine SC syringes dispensed to subjects for administration away from investigative site.

### **5.2.2.3. Nivolumab**

Nivolumab will be administered at a dose of 3 mg/kg as an IV infusion over 60 minutes every 2 weeks (Q2W). Toxicity associated with immune reactions or infusion reactions will be managed following guidance in Sections [5.4.8](#) and [5.4.9](#).

Nivolumab must be used in accordance with the storage conditions and shelf life in the manufacturer's approved label.

## **5.3. Treatment Compliance**

### **5.3.1. Treatment Compliance With INCB059872**

Compliance with all study-related treatments should be emphasized to the subject by the site personnel, and appropriate steps should be taken to optimize compliance during the study. Compliance with INCB059872 will be calculated by the sponsor based on the drug accountability documented by the site staff and monitored by the sponsor/designee (tablet

counts). Subjects will be instructed to bring all study drugs with them to the study visits in order for site personnel to conduct tablet counts to assess study drug accountability. The drug accountability documentation will be used by the sponsor to calculate treatment compliance.

### **5.3.2. Treatment Compliance With ATRA, Azacitidine, and Nivolumab**

Compliance with ATRA will be calculated by the sponsor based on the drug accountability documented by the site staff and monitored by the sponsor/designee (tablet counts). Subjects will be instructed to bring all study drugs with them to the study visits in order for site personnel to conduct tablet counts to assess study drug accountability. The drug accountability documentation will be used by the sponsor to calculate treatment compliance.

Azacitidine and nivolumab may be administered as an IV infusion by site personnel. Receipt of infusions will be documented by the site staff and monitored by the sponsor/designee.

Azacitidine may also be administered SC away from the investigative site and should be documented to ensure drug accountability.

## **5.4. Treatment Interruptions and Adjustments**

### **5.4.1. Dose Modifications of INCB059872**

Selections and modifications to the study drug regimen are planned for dose-escalation cohorts. Dose interruptions and modifications also may occur for individual study subjects. The identification of DLTs will define the doses used in planned cohorts. Further, the occurrence of DLTs and other toxicities (related or unrelated to study drug) will guide decisions for treatment interruptions and discontinuation for individual subjects.

Subjects enrolled in the dose-escalation portion of the study will have the option of escalating to a dose found to be tolerated in a subsequent cohort either within the same or alternative regimen.

Subjects enrolled in TG C and TG D who have a bone marrow blast response (at least MFLS for AML, and CR or Marrow CR for MDS) may be able to explore different and less intensive dosing regimens to allow for hematologic recovery, especially platelet recovery, as approved by the medical monitor, such as switching from QD dosing to QOD dosing. If the subject shows signs of losing the response and if deemed safe by the investigator, then the subject is allowed to revert to the prior dose and dosing schedule, but a more intensive dosing regimen than the starting dose is not allowed.

Dosing modifications due to response only is not allowed during the DLT evaluation period. In addition to dose interruption and reduction, dosing schedule modification (eg, switching from QD to QOD dosing) is also allowed for toxicity management per medical monitor approval.

### **5.4.2. Dose Modifications of Conventional Care Agents**

Decisions regarding dose reduction of conventional care agents (ATRA, azacitidine, nivolumab) should be made following the guidelines in [Table 5](#) and in consultation with the sponsor's medical monitor, taking into account relatedness of the AE to the study drug and the subject's underlying condition as well as in accordance with local prescribing information.

### 5.4.3. Dose-Limiting Toxicity and Determination of Maximum Tolerated Dose of INCB059872

Dose-limiting toxicity will be defined as the occurrence of any of the toxicities in Table 4 occurring up to and including Day 28, except those with a clear alternative explanation (eg, disease progression) or transient ( $\leq$  72 hours) abnormal laboratory values without associated clinically significant signs or symptoms based on investigator determination. All DLTs will be assessed by the investigator using CTCAE v4.03 criteria (NCI 2010). Subjects who receive at least 75% of the planned doses (eg, 11 of 14 doses for QOD schedule) of study drug at the level assigned or have a DLT will be considered evaluable for determining tolerability of the dose. Subjects who cannot complete 75% of the planned doses of study drug for reasons not due to toxicities related to study drug will not be considered evaluable for the purposes of determining the MTD and will be replaced.

Individual subject dose reductions may be made based on events observed at any time during treatment with study drug; however, for the purposes of dose cohort escalation/de-escalation, expanding a dose cohort, and determining the MTD of INCB059872, decisions will be made based on events that are observed from the first day of study drug administration through and including the final day of Cycle 1 (Day 28). A lower MTD may subsequently be determined based on relevant toxicities that become evident after Day 28.

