**Table 4: Definition of Dose-Limiting Toxicity**

Nonhematologic toxicity

Any <math>\geq</math> Grade 3 nonhematologic toxicity EXCEPT:

Transient (<math>\leq</math> 72 hours) abnormal laboratory values without associated clinically significant signs or symptoms.

Nausea, vomiting, and diarrhea adequately controlled with medical therapy within 48 hours.

An event clearly associated with the underlying disease, disease progression, a concomitant medication, or comorbidity.

Singular or nonfasting elevations in blood glucose (ie, blood glucose excursions will be considered toxicities if fasting blood glucose is elevated on 2 separate occasions).

Hematologic toxicity

Anemia : Grade 4, unexplained by underlying disease

Neutropenia:

For solid tumors: Grade 4 that does not recover to <math>\leq</math> Grade 3 in <math>\leq</math> 7 days after dose interruption.

For AML/MDS/MF: Grade 4 with a hypocellular bone marrow lasting <math>\geq</math> 6 weeks after the start of a course in the absence of residual disease.

Febrile neutropenia (for solid tumors only): absolute neutrophil count <math>< 1.0 \times 10^9/L</math> with a single temperature of <math>> 38.3^\circ C</math> (<math>101^\circ F</math>) or a sustained temperature of <math>\geq 38^\circ C</math> (<math>100.4^\circ F</math>) for more than 1 hour.

Thrombocytopenia:

For solid tumors: Any Grade 4 or Grade 3 with bleeding or any requirement of platelet transfusion.

For AML/MDS/MF: Grade 3 or higher with clinically significant bleeding or any requirement of platelet transfusion outside of institutional practice.

Other toxicities not meeting criteria above

While the rules for adjudicating DLTs in the context of dose escalation are specified above, an AE not listed above may be defined as a DLT after a consultation with the sponsor and investigators, based on the emerging safety profile.

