#### **5.4.6. Procedures for Cohort Review and Dose Escalation**

Telephone conferences will be scheduled by the sponsor with study investigators in order to review cohort-specific data and overall safety data, to agree on dose escalation, adjudicate individual high-grade AEs as potentially dose-limiting, and guide other major study decisions.

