#### **5.4.7. Criteria and Procedures for Dose Interruptions and Adjustments of INCB059872**

Study treatment may be delayed up to 2 weeks (14 days) to allow for resolution of toxicity with the exception of irAEs in subjects enrolled in TG E/E1 (see [Table 6](#) for the management of irAEs). Subjects may resume treatment if no medical condition or other circumstance exists that, in the opinion of the investigator, would make the subject unsuitable for further participation in the study. The treating investigator should contact the sponsor to discuss the case of any subject whose treatment has been delayed for more than 14 days before restarting study treatment.

Because subjects may enter the study with extensive pretreatment and/or severe bone marrow infiltration by the primary disease, these dose reduction rules are provided as guidelines (see [Table 5](#)). Individual decisions regarding dose reduction should be made using clinical judgment and in consultation with the sponsor's medical monitor, taking into account relatedness of the AE to the study drug and the subject's underlying condition. Adverse events that have a clear alternative explanation or transient ( $\leq 72$  hours) abnormal laboratory values without associated clinically significant signs or symptoms may be exempt from dose-reduction rules.

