### **9.2.2. Dose-Limiting Toxicities**

The DLTs will be listed by treatment groups defined in Section 5.2 and dose levels for subjects in Parts 1 and 3.

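### Protocol 5.4.3 lets brief, symptom-free laboratory values be waived for any DLT, but Table 4 allows this only for nonhematologic toxicity and counts Grade 4 platelets (solid tumors) and Grade 4 anemia at any duration

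*Protocol*

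**What the plan says.** Protocol 5.4.3 opens: "Dose-limiting toxicity will be defined as the occurrence of any of the toxicities in Table 4 occurring up to and including Day 28". It then takes out two classes: events with a clear alternative explanation, and transient (72 hours or less) "abnormal laboratory values without associated clinically significant signs or symptoms based on investigator determination". Nothing in the sentence ties either class to one part of Table 4.

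Table 4 prints the laboratory exception once, in the list under Grade 3 or higher nonhematologic toxicity: transient "abnormal laboratory values without associated clinically significant signs or symptoms". Its hematologic block has no such line and sets conditions row by row:

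- Neutropenia, solid tumors: "For solid tumors: Grade 4 that does not recover to" Grade 3 or lower within 7 days of interruption. For AML/MDS/MF the condition is 6 weeks or more with a hypocellular marrow.
- Thrombocytopenia: "For solid tumors: Any Grade 4 or Grade 3 with bleeding or any requirement of platelet transfusion". For AML/MDS/MF, clinically significant bleeding or an out-of-practice transfusion is needed.
- Anemia: Grade 4 that the underlying disease does not explain.

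The solid-tumor Grade 4 platelet criterion and the anemia row carry no duration.

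Three other places come near the question. Protocol 5.4.6 provides calls to "adjudicate individual high-grade AEs as potentially dose-limiting, and guide other major study decisions". Protocol 5.4.7 says that transient "abnormal laboratory values without associated clinically significant signs or symptoms may be exempt from dose-reduction rules", which concerns a subject's dose and not DLT status. SAP 9.2.2 says only: "The DLTs will be listed by treatment groups defined in Section 5.2 and dose levels for subjects in Parts 1 and 3". None of them says whether the 5.4.3 sentence or the Table 4 row prevails.

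**The concern.** The DLT count is the only input to two decision rules: the 3 + 3 rule in Parts 1 and 3 (Protocol 4.1.1 and 4.1.3), and the Cycle 1 stop in Part 2 at 5 or more DLTs in the first 15 subjects (Protocol 4.1.2). If two sites can classify the same event differently and each cite the protocol, those rules do not have a fixed input. The difference runs one way. Following 5.4.3 literally can only remove events that Table 4 counts, so any error favors the dose. Thrombocytopenia is also the toxicity the sponsor expects: Protocol 1.6.2 reports that escalation of the every-other-day schedule in TG B stopped after a Grade 4 thrombocytopenia DLT at 4 mg.

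**Working it through.** **Step 1. Where the two texts disagree.** Take a Cycle 1 event that lasts 72 hours or less, has no clinically significant signs or symptoms, no transfusion and no clear other cause.

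| Event | Table 4 row alone | 5.4.3 exception applied to all rows |
|---|---|---|
| Grade 3 or higher nonhematologic laboratory value | Not a DLT | Not a DLT |
| Grade 4 platelets, solid tumor | DLT | Can be waived |
| Grade 4 anemia unexplained by disease | DLT | Can be waived |
| Grade 4 neutropenia, solid tumor | Not a DLT (7-day limit not reached) | Not a DLT |
| Grade 4 neutropenia, AML/MDS/MF | Not a DLT (6-week limit not reached) | Not a DLT |
| Grade 3 or 4 platelets, AML/MDS/MF | Not a DLT (no bleeding or transfusion) | Not a DLT |

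The clear disagreements are the solid-tumor Grade 4 platelet count and Grade 4 anemia. Criteria that rest on bleeding or transfusion involve more than a laboratory value and are little affected.

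**Step 2. Effect of one waived event at the boundary**, assuming the subject stays evaluable (75% of doses taken).

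- 3 + 3: 2 of 6 means the MTD is exceeded; 1 of 6 allows escalation. Likewise 2 of 3 becomes 1 of 3, so the cohort is expanded instead of the dose being judged too toxic.
- Part 2: 5/15 = 33.3% stops enrollment; 4/15 = 26.7% does not.

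**Step 3. The plan's own figures.** Protocol Table 11 follows from P(escalate) = (1 − p)^3 + 3p(1 − p)^5, where p is the rate of events counted as DLTs.

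- p = 0.10: 0.7290 + 0.1771 = 0.906 (stated 90.6%)
- p = 0.20: 0.5120 + 0.1966 = 0.709 (stated 70.9%)
- p = 0.40: 0.2160 + 0.0933 = 0.309 (stated 30.9%)

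Table 11 is correct. The formula uses the counted rate. If a share s of Table 4 DLTs were waived, p would become p(1 − s). The documents give no value for s. At s = 0 nothing changes.

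**Step 4. Could the schedule show a duration of 72 hours or less?** Nominal Cycle 1 hematology draws in Protocol Table 8 are on Days 1, 4, 8, 11, 15 and 22, so the gaps are 3, 4, 3, 4 and 7 days. Bracketing an event needs a draw before it and a draw after it. The shortest such span around a scheduled draw is 7 days (for example Day 4 to Day 11). A claim of 72 hours or less would usually need an unscheduled draw.

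**The case against.** The strongest reply is that the texts can be read together: 5.4.3 is a general carve-out applied to a list, and Table 4 does not say that its rows override it. That reading is possible, but neither document states it, and the opposite reading is equally open.

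One might infer that the sponsor meant to keep the exception out of the hematologic rows, because printing it in the nonhematologic block would otherwise be redundant. The documents do not support that inference. The other 5.4.3 exception, for a clear alternative explanation such as progression, is also repeated in that block, and nobody would count a platelet drop plainly due to progression as a DLT. Repetition is simply how the section is drafted. The word 'any' before Grade 4 may also mean with or without bleeding, not at any duration.

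The qualifying set may be very small. A count that moves from Grade 4 to Grade 3 is still abnormal, so read strictly the whole abnormality must clear within 72 hours. Protocol 1.6.1 describes partial or full reversal over 4 weeks in animals. This stands, and it limits the frequency.

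The six platelet DLTs in TG B (Protocol 1.6.2) might be taken as six events open to waiver. They are not shown to be. They are described as Grade 3 or higher, and only one, at 4 mg QOD, is identified as Grade 4. A Grade 3 platelet DLT needs bleeding or transfusion and falls outside this case. All six were counted.

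Adjudication calls, the internal safety board and the power to lower the MTD later are real safeguards. None of them supplies a rule for choosing between the two texts.

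**Conclusion.** The mismatch is certain from the text; its consequence is not. This is a minor wording error in a definition that feeds dose decisions, not a design choice and not evidence of a wrong dose. It bears on Grade 4 platelets in the solid-tumor groups and, through the anemia row, on any group.

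The size that can be stated is the boundary effect: one event, 2 of 6 to 1 of 6 or 5 of 15 to 4 of 15, always toward tolerability.

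Two stronger readings are tempting, and the documents support neither.

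- *That operating characteristics shift by a known amount.* If 25% of DLTs were waived at a true rate of 20%, the counted rate would be 0.20 × 0.75 = 0.15. The 3 + 3 chance of judging the dose too toxic would fall from 29.1% to 18.6%, and the 5-of-15 stop from 16.4% to 6.2%. The 25% is invented and is applied to all DLTs, although only two kinds of event are exposed. The figures show how the rules respond to a lower rate, not what this wording does.
- *That the selected solid-tumor dose is in doubt.* Protocol 1.6.2 reports no DLTs and no Grade 3 or 4 thrombocytopenia in the 6 subjects at 3 mg QOD, so there was no platelet event of this kind to waive there. No past event is shown to be miscoded.

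The documents also do not show which cohorts were still open at Amendment 8.

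**What to change.** In Protocol 5.4.3, limit the 72-hour exception to *abnormal nonhematologic laboratory values*, and add: *Hematologic DLTs are defined by the Table 4 rows as written.* Keep the clear-alternative-explanation exception for all rows.

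If the sponsor does intend the exception for a hematologic value, write it into that Table 4 row. State the level to which the value must recover, and require a repeat count within 72 hours, since the scheduled draws would usually not show it.

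Cost: one clause and one sentence at the next amendment, with no added subjects or visits. The downside is that slightly more events may count as DLTs. The fallback adds an occasional repeat blood count.

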#### **4.1.3. Combination Dose-Finding (Part 3)**

Part 3 enrollment will be initiated after the MTD has been determined in Part 1 and will include dose-finding to evaluate safety and tolerability of the combinations. Enrollment of Part 3 will occur in parallel with Part 2. Dose-finding will use a 3 + 3 design to evaluate different doses of INCB059872 in combination with other therapies in the following treatment groups:

- Combination TG C: INCB059872 in combination with ATRA in subjects with relapsed/refractory AML. The starting dose for INCB059872 in this cohort will be 2 mg QD (2 dose levels below the recommended dose for monotherapy expansion in TG A1).
- Combination TG D: INCB059872 in combination with azacitidine in subjects with newly diagnosed, treatment-naive AML or MDS with at least 5% bone marrow blasts and IPSS-R intermediate or higher risk disease who are unfit to tolerate standard intensive chemotherapy at study entry and who are eligible to receive azacitidine as first-line therapy for the disease under study. The starting dose for INCB059872 in

this cohort will be 2 mg QD (2 dose levels below the recommended dose for monotherapy expansion in TG A1).

- Combination TG E: INCB059872 in combination with nivolumab in subjects with advanced SCLC who previously progressed on platinum-based treatment. The starting dose for INCB059872 in this cohort will be 3 mg QOD (the recommended dose for monotherapy expansion in TG B1).

The starting dose of INCB059872 in the combination treatment groups was based upon the tolerability of INCB059872 monotherapy identified in Part 1 of this study. Doses of the combination agents will be selected from conventional dose regimens and will remain the same for all dose-finding and dose-expansion cohorts. INCB059872 doses will not exceed the monotherapy MTD identified in Part 1. A minimum of 3 subjects will initially be enrolled in each treatment group in Part 3, and each subject will be observed for a DLT observation period of 1 cycle (28 days) before the next dose cohort or expansion to Part 4 begins enrollment. Subjects must have taken at least 75% of the cohort-specific dose (at least 11 doses for QOD schedule or at least 21 doses for QD schedule) in the first 28 days of study treatment or have had a DLT to be considered evaluable. Subjects who are not evaluable will be replaced.

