### **4.3.2. Replacement of Subjects**

In Parts 1 and 3, if a subject is not evaluable (ie, did not receive at least 75% of cohort-specific dose within the first 28 days of study treatment), another subject will be enrolled at this dose level. Subjects who report DLTs will be considered evaluable for the purpose of determining the safety and tolerability of the dose.

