**Table 5: Guidelines for Interruption and Restarting of Study Drug**

Chemistry			
Adverse Event		Action Taken	

 
AST and/or ALT is <math>> 3.0 \times</math> ULN and <math>< 5.0 \times</math> ULN; repeat in 1 week and if persistent or increasing or
 
AST and/or ALT is <math>> 5.0</math> AND <math>< 20 \times</math> ULN
 
 
Note: In subjects with liver metastasis-related elevations as baseline, contact sponsor to discuss clinical management and possible dose reductions.
		
 
Interrupt study drug up to 2 weeks (14 days) until the toxicity has resolved to <math>\leq</math> Grade 1 except by approval of the medical monitor.
 
Restart study drug at same dose and monitor as clinically indicated. If rechallenge is positive with AST and/or ALT elevation <math>> 3.0 \times</math> ULN, restart study drug at next lower dose (or at 25% reduction, rounded down to the nearest pill strength); monitor as clinically indicated.
 
	

 
AST and/or ALT is <math>> 20 \times</math> ULN
 
ALT <math>> 3.0 \times</math> ULN, alkaline phosphatase <math>< 2 \times</math> ULN, and bilirubin <math>\geq 2.0 \times</math> ULN (Hy's Law) and no other immediately apparent possible cause of aminotransferase elevation and hyperbilirubinemia, including, but not limited to, viral hepatitis, pre-existing chronic or acute liver disease, or the administration of other drug(s) known to be hepatotoxic.
 
		Discontinue treatment. Discontinue treatment.	
Hematology			
Parameter	Tumor Types	Adverse Event	Action Taken
Platelets ( $\times 10^9/L$ )	Solid tumors	$\geq 25$ to $< 50$	
 
If symptomatic (eg, clinically significant bleeding), discontinue.
 
If asymptomatic, hold until resolved to <math>\geq 75</math> and restart study drug at next lower dose and monitor.
 

		$< 25$	
 
If symptomatic (eg, clinically significant bleeding), discontinue.
 
If asymptomatic, hold until resolved to <math>\geq 75</math>, then restart study drug at next lower dose and monitor.
 

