**6. Section 5.4.6, Criteria and Procedures for Dose Interruptions and Adjustments of INCB059872**

**Description of change:** Table 2 (Guidelines for Interruption and Restarting of Study Drug) was revised to include discontinuation rules for Grade 4 events (asymptomatic versus symptomatic) and interruption and restarting rules for Grade 3 events. This was applied throughout the table. Language was also added to the table to clarify that granulocyte colony-stimulating factor is allowed in the management of neutropenia for low ANC in solid tumors.

**Rationale for change:** Per FDA request.

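### In the 3+3 parts, a subject under-dosed by toxicity that is not a DLT is replaced under most sections, falls outside the replacement rule of 5.4.3, and is scored by none

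*Protocol*

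**What the plan says.** **Broad rule.** Protocol Section 4.1.3 (Part 3) makes a subject evaluable with at least 75% of the doses in 28 days (11 on QOD, 21 on QD) or a DLT, and continues: "Subjects who are not evaluable will be replaced". Section 4.1.1 (Part 1) and the synopsis use the same wording. Section 4.3.2, for Parts 1 and 3, calls a subject non-evaluable who "did not receive at least 75% of cohort-specific dose within the first 28 days of study treatment" and enrols another at that dose level; subjects with a DLT stay evaluable. None of these asks why doses were missed.

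**Narrow rule.** Section 5.4.3 starts from the same test: subjects with at least 75% of the planned doses "of study drug at the level assigned or have a DLT will be considered evaluable for determining tolerability of the dose". It then says that those who cannot complete 75% "for reasons not due to toxicities related to study drug will not be considered evaluable" for finding the MTD, and that they are replaced.

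**Scoring.** Table 4 has no criterion for doses missed because of toxicity. It only allows an unlisted AE to be made a DLT after consultation. The SAP defines full-analysis, safety and PK populations (Section 5.3) and lists DLTs (Section 9.2.2). It has no DLT-evaluable set.

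**The concern.** A 3+3 cohort has 3 to 6 subjects, so one subject's classification can decide the next step. A subject who could not take three-quarters of the assigned doses because of toxicity is evidence about the tolerability of that dose. If that subject is replaced, the evidence leaves the count and the escalation decision leans towards subjects who tolerated the drug. If different sections give different answers, two cohorts with identical experience can be handled differently.

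Both dose-finding parts share the wording. Section 4.1.2 already fixes the Part 2 doses, so the exposure lies chiefly in Part 3: escalation from 2 mg QD with ATRA or azacitidine, and the judgment that 3 mg QOD with nivolumab is tolerable.

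**Working it through.** **1. The rules side by side, for a subject below 75% of doses**

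| | No DLT, cause unrelated to toxicity | No DLT, cause is study-drug toxicity | DLT |
|---|---|---|---|
| 4.1.1, 4.1.3, 4.3.2, synopsis | replaced | replaced | evaluable |
| 5.4.3 | replaced | meets neither evaluability test; not in the replacement sentence; score not stated | evaluable |

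The middle column is the conflict.

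**2. Whether the protocol's own dosing rules can produce this subject**

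- *Solid tumors.* For asymptomatic platelets of 25 to <50, Table 5 says to hold until recovery to at least 75 "and restart study drug at next lower dose and monitor". The Table 4 criterion is narrower: "For solid tumors: Any Grade 4 or Grade 3 with bleeding or any requirement of platelet transfusion". That this platelet band is Grade 3 is inferred: the Amendment 1 entry in Appendix K describes the table as holding "interruption and restarting rules for Grade 3 events".
- *AML/MDS.* A suspected drug-related platelet fall of more than 50% to below 25 calls for a hold and/or reduction (Table 5). It is a DLT only with clinically significant bleeding or transfusion outside institutional practice (Table 4).
- *Dose count.* Section 5.4.3 counts doses at the assigned level. QOD doses fall on Days 1, 3, ..., 27, so dose 11 is on Day 21. A hold that starts before that dose, followed by a restart at a lower dose, leaves at most 10/14 = 71.4%. For QD it leaves at most 20/28 = 71.4%. The 14-day hold allowed in Section 5.4.7 leaves 7/14 or 14/28 = 50%.

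**3. Size of the effect**

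The chance that a cohort passes at DLT probability p is f(p) = (1−p)³ + 3p(1−p)²·(1−p)³. At p = 10, 20, 30, 40, 50 and 60% this gives 90.6, 70.9, 49.4, 30.9, 17.2 and 8.2%. All six values of Protocol Table 11 are reproduced.

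Let D be the share of subjects with a counted DLT. Let q be the further, non-overlapping share below 75% because of toxicity not counted as a DLT. **The documents do not give q; it is assumed.** Then p = D/(1−q) if these subjects are replaced, p = D if they are kept as non-DLTs, and p = D+q if they are counted as DLTs.

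Example, D = 20%, q = 10%, replaced: p = 0.20/0.90 = 0.222, and f = 0.778³ + 3 × 0.222 × 0.778⁵ = 0.470 + 0.190 = 0.660.

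| D | q | Replaced | Kept as non-DLT | Counted as DLT |
|---|---|---|---|---|
| 10% | 10% | 88.7% | 90.6% | 70.9% |
| 10% | 20% | 86.2% | 90.6% | 49.4% |
| 20% | 10% | 66.0% | 70.9% | 49.4% |
| 20% | 20% | 60.0% | 70.9% | 30.9% |
| 30% | 10% | 42.8% | 49.4% | 30.9% |

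Keeping these subjects as non-DLTs makes passing more likely than replacing them does. Aligning the other sections with 5.4.3 without a scoring rule could therefore make matters worse.

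**4. Evidence on q in the documents**

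All 3 TG B subjects at 3 mg QD were interrupted and reduced in Cycle 1 (Table 3, footnote b), and Section 1.6.2 reports 2 DLTs there. At least 1 of 3 was thus reduced without a DLT (exact 95% CI 0.8% to 90.6%). The doses that subject took, and the cause and timing of the reduction, are not given.

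**The case against.** **The conflict is only implied.** Section 5.4.3 opens with the same test as the other sections and never says that a toxicity-limited subject must not be replaced. One can read everything consistently: below 75% without a DLT is non-evaluable, hence replaced. The Amendment 4 entry in Appendix K says that the evaluability text of 4.1.1, 4.1.3 and 4.3.2 was clarified on FDA recommendation, which suggests that those sections govern. This stands as a limit on the wording of the point. It does not remove the problem: that reading makes the restriction in 5.4.3 idle, and it is the reading that discards the intolerance.

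**The larger gaps depend on a rule the protocol does not contain.** Replacing and keeping as non-DLT differ by 70.9 − 66.0 = 4.9 points at D = 20%, q = 10%. Only counting as a DLT moves the chance further. This is correct, and the table should be read accordingly.

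**An automatic DLT would override deliberate definitions.** Table 4 leaves out uncomplicated Grade 3 thrombocytopenia in solid tumors. Under an automatic rule, a hold just before the Day 21 dose would be a DLT and the same event on Day 22 would not. Section 5.4.7 adds that "these dose reduction rules are provided as guidelines". This stands, and it is why the fix needs an exception through cohort review.

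**Safeguards exist.** INCB059872 may not exceed the Part 1 MTD (4.1.3). Cohort calls adjudicate high-grade AEs (5.4.6), unlisted AEs may be made DLTs (Table 4), later toxicity may lower the MTD (5.4.3), and the sponsor, investigators and iDSMB review safety (8.7). These limit the harm. None says how to score the subject.

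**Conclusion.** The point holds and should be fixed. The sections give different replacement rules for a subject under-dosed by study-drug toxicity without a DLT, none says how to score that subject, and the broader wording removes the subject from the count. This rests on the text alone. The size rests on an assumed q and is illustrative; the safeguards above make the practical consequence limited.

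Four stronger readings are tempting and are not supported:

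- *That 5.4.3 forbids replacing such a subject.* It does so only by implication.
- *That this is a Part 3 problem.* Sections 4.1.1 and 4.3.2 and the synopsis carry the same rule for Part 1.
- *That Part 1 shows it happening.* The 3 mg QD data are preliminary, the third subject's dosing is unknown, and 2 DLTs in 3 subjects had already settled that cohort's decision.
- *That partner-drug toxicity would be excused as a concomitant medication or alternative explanation.* Table 6 treats nivolumab as a study drug, SAP Section 4.2.3 confines concomitant medication to nonstudy drugs, and the only example of an alternative explanation in 5.4.3 is disease progression. Protocol Section 7.4 words concomitant medication broadly, but nothing shows that such an event would be excused.

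**What to change.** Use one rule in Sections 4.1.1, 4.1.3, 4.3.2 and 5.4.3 and in the synopsis:

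1. Replace a subject below 75% only when the reason is unrelated to toxicity of the assigned regimen, meaning INCB059872 or, in Part 3, its partner.
2. A subject below 75% at the assigned level in the first 28 days because of such toxicity is not replaced and counts as a DLT by default. The exception is where the Section 5.4.6 cohort review documents, before escalation, why the event is not dose-limiting; an example is a brief protocol-directed hold for an asymptomatic event that Table 4 deliberately excludes.
3. Optional: state that the assigned partner drug is not an alternative explanation for a DLT.

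The drafting cost is a few sentences in an amendment. The operating cost is that some cohorts expand or stop more often, also at tolerable doses. If every such subject were counted, then at D = 10% the chance of passing would fall from 88.7% to 70.9% at q = 10%, and from 86.2% to 49.4% at q = 20%. The documented exception reduces this loss.
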